4.4.6 Fistula Thrombosis Within the First Six Weeks Following Fistula Creation Surgery

If fistula thrombosis occurs prior to randomization, the patient should not be randomized to treatment group and study participation will end. If fistula thrombosis occurs after randomization, study drug will be discontinued. Study drug should not be discontinued for thrombosis unless thrombosis is confirmed by a member of the study team or by the patient's surgeon. The duration of study participation after fistula thrombosis will depend on whether fistula patency is restored. If fistula patency is not restored, study participation will end 30 days after the study drug is discontinued. If fistula patency is restored, the patient will remain off the study drug, but participation in the study will continue until the ascertainment of fistula suitability for dialysis.

4.5 Study Completion

Participation in the study will end once the fistula suitability for dialysis outcome has been ascertained. This ascertainment will be completed by 150-180 days after fistula creation for patients already on chronic dialysis at the time of fistula creation and for patients who begin chronic dialysis within 120 days after fistula creation. For patients who start chronic dialysis >120 days following creation of the AV fistula, ascertainment of fistula suitability for dialysis will be completed by 30-60 days after the start of chronic dialysis. However, if the fistula has not been used at the time of the suitability assessment, but may be used in the future, the patients will continue to be followed until it is determined whether the fistula is actually used. For patients who do not start hemodialysis by the end of the study period, the fistula suitability outcome will not be ascertained and completion of study participation will coincide with the end of the study.

If fistula thrombosis occurs prior to the ascertainment of fistula suitability for dialysis, and if fistula patency is not restored, study participation will end at the time of fistula thrombosis or 30 days after study drug discontinuation, whichever comes later. Fistula thrombosis must be confirmed by a member of the study team or the patient's vascular surgeon. If fistula thrombosis occurs prior to the ascertainment of fistula suitability for dialysis, and if fistula patency is restored, participation in the study will end once the fistula suitability for dialysis outcome has been ascertained.

Data collection after study participation has ended will include hospitalization and mortality data obtained from national databases while the study is on-going and for up to five years after the study has ended.

5. DATA COLLECTION

5.1 Baseline Data

The baseline evaluation is designed to ensure that subjects meet the inclusion/exclusion criteria, to obtain information regarding demographics, access history, dialysis prescription, and medical history that may affect treatment response and risk of access thrombosis, and to obtain a laboratory evaluation to ensure that patients are not at risk for developing complications of therapy. Data should be collected as close to the time of fistula creation as possible but no longer than 45 days prior, and should include:

1. Demographic Data – age, gender, racial/ethnic background.
2. Medical History – cause of ESRD, diabetes mellitus, hypertension, myocardial infarction, angina, congestive heart failure, cerebrovascular accident or transient ischemic attack, claudication, amputation, smoking history, deep venous thrombosis or pulmonary embolism, nephrotic syndrome, significant bleeding event within past year, peptic ulcer disease.
3. Height and weight (for determination of body mass index).
4. Access History – number, type, and location of any previous accesses.
5. Dialysis History – date of initiation of chronic dialysis, if currently on dialysis.
6. Current Medications
7. Blood Pressure (sitting) – For patients already on dialysis, this should be a pre-dialysis, mid-week measurement.
8. Laboratory Data – CBC. For patients on dialysis, the blood should be drawn pre-dialysis. Laboratory tests should be done no longer than 45 days prior to randomization.
9. Quality of life

5.2 Blood and DNA Collection

Blood and DNA samples will be collected for use in future research studies to assess risk factors for access failure and response to therapy. A sample (30 ml) will be collected once for each patient, preferably at the baseline visit. For those patients where this is not possible, collect the blood at the next possible visit.

5.3 Six Weeks After Fistula Creation

1. Fistula Anatomy – date of surgery, site of anastomosis (e.g., wrist, elbow), inflow artery, outflow vein.
2. Fistula Patency – presence of bruit throughout systole and diastole ≥ 8 cm proximal to the arteriovenous anastomosis
3. Current Medications
4. Intercurrent /Adverse Events – drug reactions, side effects, hospitalizations, death, access procedures (fistulogram, angioplasty, thrombectomy, conversion to graft, ligation of draining veins), abnormal laboratory values, or other complications. The occurrence of any such events should be reported as close to the time the event occurred as possible;

however, the review at this study visit should minimize the possibility that such events go unrecognized or unreported. Patients will be instructed at enrollment to inform study personnel immediately if a bleeding event occurs.

5. If dialysis was initiated via the new fistula prior to this six-week study visit the date of initiation of dialysis should be recorded.
6. Procedures performed on fistula (fistulogram, angioplasty, thrombectomy, conversion to graft, ligation of draining veins), and dates of such procedures.
7. Study Drug Use – reason for and duration of study drug interruption. Remaining study drug should be returned at this visit and pill count performed.
8. Quality of life

For patients with fistula thrombosis and no restoration of patency during the six week study drug administration period, all of the above data (#'s 1-8) will be collected at the earlier of the following: six weeks after fistula creation or at the end of study participation (30 days after discontinuation of study drug).

5.4 Follow-up Data

After the six-week study visit, contact will be made by the study coordinator with study subjects, their physicians, their dialysis units, and other sources on a monthly basis to capture data on interim events and to ascertain secondary outcomes. The data to be collected include:

1. Date of first cannulation of fistula.
2. Date at which fistula is used for four weeks of consecutive dialysis treatments.
3. Minimum dialysis machine blood flow rate during the 12 dialysis sessions prior to study completion. The minimum blood flow rate should be determined from the blood flow measurements recorded after the first hour and before the last 15 minutes of the dialysis session. Study completion will occur 5 months after fistula creation for patients who are on dialysis at the time of fistula creation or start dialysis within 4 months of fistula creation. Study completion will occur 4 weeks after dialysis initiation for patients who start dialysis >4 months after fistula creation. However, if the fistula has not been used at the time of the suitability assessment, but may be used in the future, the patients will continue to be followed until it is determined whether the fistula is actually used.
4. Procedures performed on fistula (fistulogram, angioplasty, thrombectomy, conversion to graft, ligation of draining veins), and dates of such procedures.
5. For patients not on chronic dialysis prior to creation of the fistula – date of first dialysis.
6. Intercurrent/Adverse Events - bleeding events and hospitalizations during the 30 days following end of study drug administration period. Death during the period of study participation.
7. Quality of life

For patients with fistula thrombosis and no restoration of patency during the six-week study drug administration period, quality of life data is collected as indicated in item 7.

Data collection after study participation has ended will include hospitalization data and mortality data obtained from national databases while the study is on-going and for up to five years after the study has ended.

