The third study visit will occur following ascertainment of the fistula suitability outcome. At this visit, a quality of life questionnaire will be completed⁴⁶⁻⁴⁷, procedures performed on the fistula will be documented, and adverse events will be reviewed. The patient will be informed that participation in the study has ended. Ascertainment of fistula suitability will occur during the fourth month following fistula creation for patients who are on dialysis within 4 months of fistula creation or during the first month of dialysis for patients who start dialysis > 4 months following fistula creation. The fistula suitability outcome will not be ascertained for those patients who do not start hemodialysis during the study period. If the fistula has not been used at the time of the suitability assessment, but may be used in the future, the patients will continue to be followed until it is determined whether the fistula is actually used.

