4.2 Study Drug Administration

Study drug will consist of identical tablets containing either clopidogrel 75 mg or placebo. The supply of study drug will be provided to the patient following treatment group assignment. Patients will be instructed to take the first dose of study drug by mouth - clopidogrel 300 mg (4 pills) or placebo (4 pills), within 1 calendar day following fistula creation surgery. After that, the patient will take clopidogrel 75 mg (1 pill) or placebo (1 pill) daily. Study drug will be continued until 6 weeks after fistula creation surgery.

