Management of bleeding should be handled as for a patient on aspirin. For minor episodes of bleeding (e.g., superficial abrasion or nose bleed), conservative measure to control the bleeding should suffice without the requirement for discontinuing study medication. Short-term discontinuation of study medication during an intermediate bleeding episode with re-institution when stable is allowed. If the patient has a major or life-threatening bleed the study medication will be discontinued and not restarted. In the event of a cerebrovascular accident occurring during active treatment, computed tomography or magnetic resonance imaging should be performed to exclude intracerebral hemorrhage. For intermediate bleeds the decision to stop study drug will be made by the physician(s) caring for the patient. If the patient has a major or life-threatening bleed the study medication will be discontinued and not restarted unless the bleed is caused by either a surgical procedure or trauma and it is established 1) that the cause of bleeding has been eradicated, and 2) that the bleeding event does not reflect an underlying bleeding tendency or predispose to recurrent bleeding. Study drug resumption in this situation must be approved by the physician(s) caring for the patient. Bleeding events will be actively monitored and recorded by the study coordinator throughout the patient's participation on the study. An expert panel will review all major and life-threatening bleeds as well as a randomly selected subset of other bleeding events.

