9. TREATMENT EFFECTS AND SAFETY MONITORING

An External Advisory Committee (EAC), composed of independent experts in the fields of nephrology, biostatistics, and clinical trials, will review the accumulating data with regard to

safety and efficacy. The members of the EAC are not involved in the conduct of the trial and have no affiliation with the drug manufacturers. Summary reports of the EAC will be submitted to all IRBs involved in the trial.

The EAC may terminate the trial early if one of the interventions (clopidogrel or placebo) is shown to be superior at an interim analysis based on the statistical stopping guideline (Section 8.2.1). The EAC will also consider comparisons of potential adverse events between the treatment arms. Conditional power calculations and estimates of the recruitment rate will also be provided at interim analyses so that the EAC can assess whether the trial should be terminated early in the event of unexpectedly low recruitment or trends in the treatment group comparison indicating futility of continuation of the study.

Serious adverse events are those that result in any of the following outcomes: death, a life-threatening adverse experience, inpatient hospitalization or prolongation of existing hospitalization, a persistent or significant disability/incapacity, or a congenital anomaly or birth defect. All serious adverse events are reported to the DCC within 24 hours of study personnel learning of the event. Information not available at the time of the initial report will be submitted to the DCC as a follow-up report. The DCC will be responsible for distributing safety reports to the Clinical Centers, the EAC, and NIDDK. NIDDK will submit safety information to the FDA. Summary reports of adverse events will be submitted to all IRBs monitoring the trial. Additional reporting to IRBs will be performed according to local IRB policy. Non-serious adverse events will be reported to the DCC using the appropriate data forms.

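### Bleeding and hospitalization have incompatible collection windows, and safety follow-up ends earlier for patients whose fistula clots

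*Protocol*

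**What the plan says.** The current protocol text sets the window in several places:

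- **Section 5.4, item 6** limits collection to "bleeding events and hospitalizations during the 30 days following end of study drug administration period". The same item then follows "Death during the period of study participation", so the shorter limit for bleeding and admissions appears deliberate.
- **Section 4.4.1:** "Bleeding events will be actively monitored and recorded by the study coordinator throughout the patient's participation on the study".
- **Section 4.1, third visit:** "procedures performed on the fistula will be documented, and adverse events will be reviewed", with no 30-day limit.
- **Section 9:** "All serious adverse events are reported to the DCC within 24 hours of study personnel learning of the event". Inpatient hospitalization counts as serious, and no end date is given.
- **Section 5.5** calls bleeding the major expected risk. It requires central review of any death preceded within 30 days by a bleed in the database.

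Drug lasts 42 days: "Study drug will be continued until 6 weeks after fistula creation surgery". Section 4.5 puts the end of participation at 150-180 days for patients on dialysis by day 120, and later for others.

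Unrestored thrombosis in the drug period has its own rules. Sections 4.4.4 and 4.4.6 end participation 30 days after drug stop. Section 5.3 says the six-week data, adverse events included, "will be collected at the earlier of the following: six weeks after fistula creation or at the end of study participation". For these patients Section 5.4 then names quality of life only.

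**The concern.** There are two separate problems.

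The first is which events are counted at all. Two centers that follow different sections would record different off-drug bleeds and admissions for identical patients. A later analysis plan can cut dated events at any day, but it cannot recover events that sites were not told to collect.

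The second is that observation time depends on the primary outcome. Clotting shortens safety follow-up, and if clopidogrel works, clotting is more common on placebo. A crude comparison of bleeding proportions would then observe the placebo arm for less time.

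Bleeding is what would be weighed against any gain in patency, and Section 9 has the External Advisory Committee compare adverse events between arms.

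**Working it through.** The protocol gives no figure for these windows, so none is challenged. The thrombosis rates used below come from Section 8.1: 25% on placebo and a 30% reduction, so 0.25 x 0.70 = 17.5% on clopidogrel. Those inputs approximately reproduce the stated sample size. With 3% drop-in and 3% drop-out the rates become 0.24775 and 0.17725, which needs 604 per arm (pooled variance, no continuity correction). Then 2 x 604 / 0.95 x 1.027 = 1306, which is 1.7% above 1284.

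**1. Patent fistula.** The Section 5.4 window closes at 42 + 30 = day 72. Participation under Section 4.4.1 runs to day 150-180.
- 150 - 72 = 78 days, or 52% of participation
- 180 - 72 = 108 days, or 60% of participation

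**2. Late bleed before a death.** Take a bleed on day 120 and a death on day 125. The death is captured under Section 5.4. A site following item 6 need not have recorded the bleed, so the Section 5.5 trigger may not fire.

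**3. Unrestored thrombosis, drug stopped on day s.** Participation ends on day s + 30. The last listed event review is the earlier of day 42 and day s + 30, so it precedes the end of participation when s > 12.

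| Drug stop | Participation ends | Last listed review | Post-drug days before that review |
|---|---|---|---|
| day 7 | day 37 | day 37 | 30 of 30 |
| day 28 | day 58 | day 42 | 14 of 30 |
| day 30 | day 60 | day 42 | 12 of 30 |
| day 38 | day 68 | day 42 | 4 of 30 |

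**4. Effect on the arms.** Mean window = (1 - p) x patent window + p x (s + 30), where p is the thrombosis rate. Assume no clotted fistula is reopened, drug stops on the day of the clot, all clots fall on one day, and no fistula patent at six weeks clots later. For s = 14:
- Section 5.4: placebo 0.75 x 72 + 0.25 x 44 = 65.0 days; clopidogrel 0.825 x 72 + 0.175 x 44 = 67.1 days; ratio 1.03
- Section 4.4.1, 150 days: placebo 0.75 x 150 + 0.25 x 44 = 123.5 days; clopidogrel 0.825 x 150 + 0.175 x 44 = 131.45 days; ratio 1.06

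Over clot days 1-41 the ratio runs 1.00-1.05 under Section 5.4 and 1.05-1.08 under Section 4.4.1 (150-180 days).

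If the bleeding hazard is constant and equal in both arms (assumed 5-20% over 72 days, clot day 7-28), the spurious excess on clopidogrel is 0.1-0.7 percentage points under Section 5.4. It is 0.5-2.0 points under Section 4.4.1 with 150 days.

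**5. Pooling off-drug time.** Assume a constant background rate and a raised rate on the 42 drug days. Compare 72 days with 165 days, the midpoint of 150-180.
- Doubled rate: (42 x 2 + 30)/72 = 1.58 against (42 x 2 + 123)/165 = 1.25
- 1.5-fold rate: (42 x 1.5 + 30)/72 = 1.29 against (42 x 1.5 + 123)/165 = 1.13
- Absolute excess, doubled rate: 114 - 72 = 42 and 207 - 165 = 42 background-day units

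The ratio moves toward 1, but the absolute excess does not change.

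**The case against.** The strongest reply is that every section covers the time on drug, so only off-drug events are in dispute. That stands, and it limits the size of the problem.

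A reader might infer that Section 5.3 stops event collection at week 6 for clotted patients. It does not. It dates a review, and the same section asks that events be reported close to when they occur. Sections 4.4.1 and 9 still apply until the patient leaves, and Section 5.4 does not say that quality of life is the only item collected. What remains is that no closing review is listed after week 6 for these patients.

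A reader might also infer that the longer window makes clopidogrel look safer when benefit and harm are weighed. The protocol does not support that. It does not say that the analysis pools all off-drug time, and pooling would leave the absolute excess unchanged. The unequal follow-up of clotted patients pushes the other way, against clopidogrel.

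Other replies stand in part:
- A Manual of Operations and common data forms may align the centers. With blinding and stratification by center, one center's reading should apply alike to both arms. This protects the comparison from differences between sites, but not from follow-up that depends on clotting.
- National databases (Sections 4.5 and 5.4) may recover some admissions, but not bleeds treated without admission.
- Item 6 could mean 30 days after each patient's own last dose. The protocol elsewhere uses the phrase for the six-week period, and that reading would still contradict Section 4.4.1.
- Section 8.2 names only a comparison of death rates, so bleeding is not formally the main safety comparison. Its weight comes from Sections 5.5 and 9.

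**Conclusion.** The contradiction is in the operative text and nothing in the protocol resolves it. For bleeding it lies between Sections 4.4.1 and 5.4. For hospitalization it lies between Section 5.4 and the open-ended duties in Sections 4.1 and 9. The larger consequence is inconsistent capture over 78-108 off-drug days with a patent fistula, including bleeds that the fatal-bleed review depends on.

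The dependence on clotting is real but modest: a mean-window ratio of about 1.00-1.08. That range rests on the design thrombosis rates and on no clotted fistula being reopened; reopening would shrink it. If clopidogrel had no effect on thrombosis, the imbalance between arms would disappear, but the inconsistent capture would not. The on-drug rate ratios and background bleeding rates above are assumptions. This should be corrected, but it does not undermine the primary analysis.

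**What to change.** Reconcile Sections 4.1, 4.4.1, 5.3, 5.4 and 9. Bleeding and hospitalization should be collected in every randomized patient at least to one common fixed day, for example six weeks plus 30 days after fistula creation, whether or not the fistula clotted or drug stopped early. Base the between-arm bleeding comparison on that common window.

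Make conforming edits to the participation-end rules in Sections 4.4.4, 4.4.6, 4.5 and 6, which now release patients with early clots before day 72. Add a closing event review by telephone for patients with unrestored thrombosis. The common day is a minimum for collection: do not use it to shorten serious-event reporting in Section 9 or the fatal-bleed review in Section 5.5. The rules for stopping study drug need no change for this purpose.

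The cost is wording, one extra contact, and longer safety follow-up after an early clot. With day 72 as the common day, the added time is 72 - (s + 30) = 42 - s days, for example 35 days when drug stops on day 7.

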5.5 Quality Control at the Clinical Centers

Clinical procedures will be done following the Manual of Operations. Data will be edited by automated programs at the time of data entry. At site visits, a team will check each clinical center's adherence to protocol and its patient recruitment, retention, and compliance. During a

data audit portion of each site visit, team members will compare data in the study database with source documentation for a random subset of the patients.

Bleeding is the major expected risk of therapy with clopidogrel. For purposes of safety and adverse event analyses, categorization of bleeding events will be made based on information transmitted from the Clinical Centers on the data forms with additional information obtained from source documents as needed. To assure that bleeding events that result in death are properly documented there will be central review of data on any subject who has had a bleeding event recorded in the study database within 30 days prior to death. The study's Data Coordinating Center will notify investigators about any subject who meets these criteria. The center will then send primary data including any emergency room or hospital discharge summaries relevant to the bleed as well as documentation relating to the subsequent death. This information will be reviewed by two independent physician study investigators to determine whether the cause of death was related to the prior bleed.

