4.4.1 Bleeding

Bleeding will be classified as minor, intermediate, major, life-threatening or fatal. Minor bleeding events are episodes of bleeding that do not require an event-related visit or follow-up or discontinuation of the study drug. Intermediate bleeding is a bleeding event that does not meet criteria for a major bleed but requires an event-related visit with a health care provider or temporary discontinuation of study medication. Examples of minor or intermediate bleeds might include superficial cuts, abrasions, bruises, epistaxis, or vaginal bleeding events. The presence of a hemocult positive stool alone that leads to non-emergent evaluation such as a colonoscopy and is not associated with a ≥ 2 g/dl drop in hemoglobin or the need for a transfusion will be considered an intermediate bleeding event. Major bleeding is defined as a confirmed retroperitoneal, intra-articular, intraocular, or intracranial bleed or any bleed that leads to a drop in hemoglobin by 2 g/dl and requires hospitalization or the need for a transfusion. Life-threatening bleeding is any bleed that leads to a drop in hemoglobin of ≥ 5 g/dl, requires emergency surgical intervention, causes a symptomatic intracranial hemorrhage, or requires a transfusion of more than 4 units of packed RBCs or whole blood. Fatal bleeding is any bleed that causes or precipitates death.

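### The central cause-of-death review for bleeding opens only when a bleed was recorded within 30 days before death, which is narrower than the protocol's own definition of fatal bleeding

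*Protocol*

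**What the plan says.** Section 5.5 names bleeding as the main expected risk of clopidogrel. It says bleeds are categorized from the Clinical Centers' data forms, with source documents obtained when needed. It then adds a specific check on deaths. The purpose is "To assure that bleeding events that result in death are properly documented", and the means is "central review of data on any subject who has had a bleeding event recorded in the study database within 30 days prior to death". The material is "reviewed by two independent physician study investigators to determine whether the cause of death was related to the prior bleed".

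Section 4.4.1 gives the definition: "Fatal bleeding is any bleed that causes or precipitates death". It also sets up a second route: "An expert panel will review all major and life-threatening bleeds as well as a randomly selected subset of other bleeding events".

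The protocol describes the collection of bleeds in two ways. Section 4.4.1 says "Bleeding events will be actively monitored and recorded by the study coordinator throughout" the patient's participation. Section 5.4, on the period after the six-week visit, lists "bleeding events and hospitalizations during the 30 days following end of study drug administration period", but for mortality it lists "Death during the period of study participation".

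Section 9 makes every death a serious adverse event, to be reported to the Data Coordinating Center within 24 hours of study personnel learning of it. Section 8.2.2.2 plans a comparison of death rates between the arms.

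**The concern.** The check is meant to make sure that bleeding deaths are documented, yet it starts only if a bleed has been documented. A death reported as cardiac arrest or stroke, with no bleeding form, does not open it. The 30-day limit also has no counterpart in the definition of fatal bleeding, so a bleed can meet the definition and still miss the trigger.

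Fatal bleeding is the gravest category of the harm the protocol itself puts first, and Section 9 has the External Advisory Committee weigh adverse events by arm. At stake is whether that category is centrally confirmed with the completeness that Section 5.5 sets out to achieve.

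**Working it through.** The protocol gives no statistical figure on this point, so there is none to reproduce. The check sets the sections side by side and compares windows in days.

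**1. Trigger against definition.** Inputs: the trigger in 5.5 and the definition in 4.4.1. The trigger has two conditions, a bleed in the database and an interval to death of at most 30 days. The definition has neither. Two kinds of fatal bleed therefore fall outside the trigger: those never entered as a bleed, and those that lead to death after more than 30 days. As an illustration, take an intracranial bleed on day 20 and death on day 55. The interval is 55 − 20 = 35 days, which exceeds 30, so the cause-of-death review does not open.

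**2. Does the expert panel in 4.4.1 cover the remainder?** In part.
- In the illustration, an intracranial bleed counts as major, and as life-threatening if symptomatic. The panel reviews it whatever the interval to death. Its stated object is the bleed. Cause of death is given to the two physicians in 5.5, who are not called on here.
- A bleed never entered cannot reach the panel.
- Fatal is a separate category in 4.4.1 and is not on the panel's list. Outside the named anatomical sites, a major bleed needs a documented haemoglobin fall together with hospitalization or transfusion. A life-threatening bleed needs a larger fall, emergency surgery, a symptomatic intracranial haemorrhage or a large transfusion. A patient who bleeds to death before reaching hospital may have none of these on record, so panel review is not guaranteed.

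**3. Does any other section send such deaths to central review?** Section 9 brings all deaths to the Data Coordinating Center but assigns no cause-of-death review. The site audits in 5.5 cover a random subset of patients. The comparison in 8.2.2.2 counts deaths from any cause. None of these directs a death without a recorded bleed, or a late death after one, to a central judgement on cause.

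**4. Collection windows, for a patient who completes six weeks of drug.**
- End of drug period: 6 × 7 = day 42.
- End of bleed collection as listed in 5.4: 42 + 30 = about day 72.
- Last death that can open the review on that listing: 72 + 30 = about day 102.
- Section 4.5 has suitability ascertainment completed by day 150–180 for patients on dialysis by day 120. Later dialysis starters stay longer.
- Time during which deaths are collected but new bleeds are not listed for collection: 150 − 72 = 78 days to 180 − 72 = 108 days.
- Time during which a death cannot open the review at all: 150 − 102 = 48 days to 180 − 102 = 78 days.

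This gap exists only if Section 5.4 governs. If bleeds are recorded throughout participation, as 4.4.1 says, it disappears. The two sections cannot both describe the data collection.

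**The case against.** The strongest reply is that the 30-day review is an added quality check and not the only way to identify a fatal bleed. That is correct. Under 5.5 a Clinical Center can classify a bleed as fatal at any interval, using its forms and source documents. Coordinators monitor bleeding actively, and patients are told to report bleeds at once. Contacts are monthly after week six, and deaths reach the Data Coordinating Center quickly. Section 4.4.1 calls for imaging after a stroke on treatment, which should reveal many intracranial bleeds. The wording of the trigger may also include a bleed entered together with the death report, provided it is dated within the 30 days.

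Three stronger readings are tempting, and the protocol does not support them.
- A reader might infer that bleeds outside the trigger are never adjudicated. That is wrong for recorded major or life-threatening bleeds, which go to the expert panel. What is missing is a required judgement on the link to the death.
- A reader might infer that one or two missed events would change the safety conclusion. The protocol gives neither an expected number of fatal bleeds nor a decision threshold, so this cannot be shown.
- A reader might infer a bias between arms, or an error in one direction only. Personnel are masked (3.4), and nothing shows that misses would differ by arm. The review itself cannot find omissions, but where it does not open, a site may over-call as well as under-call.

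What stands after this is the narrower point. Even on the lenient reading, someone must have recognised and entered a bleed, and no section requires central judgement on a late death.

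**Conclusion.** The point holds as a limited weakness in safety ascertainment. The cause-of-death review in 5.5 is narrower than its own purpose and than the definition in 4.4.1, so some fatal bleeds may not be centrally confirmed as fatal. How many cannot be estimated from the protocol, which gives no rate for deaths, fatal bleeds or unrecorded bleeds. The primary efficacy analysis and the all-cause death comparison are unaffected.

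The conclusion on the trigger rests on the wording alone. The further gap after about day 102 rests on Section 5.4 being the operative collection rule. This is a cheap improvement, not a flaw that threatens the trial's conclusions.

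**What to change.** 1. In 5.5, replace the trigger. The two physician reviewers, masked to treatment, review every death from randomization to 30 days after the end of the study drug period. They also review any later on-study death in a patient with a major or life-threatening bleed on file, without the 30-day limit.
2. In 4.4.1, add fatal bleeds to the list that the expert panel reviews.
3. Reconcile 4.4.1 and 5.4 on how long bleeding events are collected. This matters for the first change, because a late death with no bleed on file would still fall outside the review.

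The cost is modest reviewer time and document collection for deaths already reported as serious adverse events, using reviewers and a document route already in place. The protocol gives no death rate. If, purely as an assumption, 1–3% of the 1,284 patients died in the first window, the workload would be 1,284 × 0.01 ≈ 13 to 1,284 × 0.03 ≈ 39 deaths. Later deaths after a major or life-threatening bleed would add to this. The figure measures reviewing effort and says nothing about how many fatal bleeds are missed. The change affects ascertainment only; treatment and the efficacy analysis stay as they are.
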